8.2 Assessment of Subject Characteristics

8.2.1 Demographics

Demographic information (age, sex, ethnicity, and race) will be obtained during Screening as specified in the Study Schedule of Assessments (Section 8.1).

8.2.2 Medical and Surgical History

Medical and surgical history information will be obtained during Screening as specified in the Study Schedule of Assessments (Section 8.1).

A general medical history will be collected. In addition, the medical history will document conditions, focusing specifically on the following body systems: head, eyes, ears, nose, throat (HEENT). The medical history will also include an assessment of the subject's lifetime history of the following:

- Chronic rhinosinusitis
- Asthma
- Chronic obstructive pulmonary disease (COPD)
- Perennial rhinitis
- Seasonal allergic rhinitis (SAR)
- Sensitivity to nonsteroidal anti-inflammatory drugs (NSAIDs)
- Smoking

Subjects will also be assessed if they had the following history of surgery or injury in the past:

- Ethmoidectomy
- Polypectomy
- Nasal surgery involving nasal turbinates
- Functional endoscopic sinus surgery (FESS)
- Any known history of surgery or injury that may prevent placement or retention of LYR-220

8.3 Assessment of Safety

8.3.1 Physical Examination

A limited physical examination including a careful assessment of the head, eyes, ears, nose, and throat (HEENT), will be performed at Screening visit as specified in the Study Schedule of Assessment (Section 8.1). Height and weight will also be measured. Body mass index (BMI) will be calculated based on the measured height and weight.

8.3.2 Vital Signs

Vital signs will be measured at the screening visit as specified in the Schedule of Assessments (Section 8.1). Vital sign measurements will include blood pressure (systolic and diastolic, mm Hg), and pulse rate (beats per minute), aural/oral temperature (°C or °F), and respiration rate (breaths per minute). All measurements will be obtained after the subject has been seated for at least 5 minutes.

8.3.3 Laboratory Assessments

Laboratory testing will be performed at clinic visits as specified in the Schedule of Assessments (Section 8.1). Any unused duplicated samples collected for the purpose of this study will be destroyed after the completion of the study. Testing will be performed at a central laboratory.

8.3.3.1 Hematology

Samples for hematology assessments will be obtained during Screening and Week 25 visits as specified in the Schedule of Assessments (Section 8.1).

Hematology assessments will include white blood cell (WBC) count and WBC differential (neutrophils, eosinophils, lymphocytes, monocytes, and basophils), red blood cell (RBC) count, hematocrit, hemoglobin, and platelet count.

8.3.3.2 Blood Chemistry

Samples for blood chemistry assessments will be obtained during Screening and Week 25 visits as specified in the Schedule of Assessments (Section 8.1).

Clinical blood chemistry laboratory analytes will include electrolytes (sodium, potassium, chloride, and bicarbonate), blood urea nitrogen, serum creatinine, glucose, total bilirubin, aspartate aminotransferase, alanine aminotransferase, alkaline phosphatase, lactate dehydrogenase, uric acid, total protein, albumin, calcium, magnesium, and phosphate.

8.3.4 Nasal Endoscopy Assessments

Ethmoid cavities will be assessed by endoscopy during Screening, on Day 1 prior to LYR-220 administration procedure, and at Week 4, 12, 24/EOT (before LYR-220 removal), and 25 visits as specified in the Schedule of Assessments (Section 8.1).

Local safety evaluation of ethmoid cavity will be performed on Day 1 prior to LYR-220 administration procedure and at Week 4, 12, 24/EOT, and 25 visits to document presence of epistaxis, mucosal injury, and any other adverse local observations in ethmoid cavity.

The severity of epistaxis will be determined by the Investigator on the basis of his or her clinical judgment and the following definitions:

- Mild: blood-tinged mucus, nonactive nose bleeding
- Moderate: active nose bleeding that does not require medical intervention
- Severe: frank nose bleeding that requires medical intervention

The severity of mucosal injury will be determined by the Investigator on the basis of his or her clinical judgment and the following definitions:

- Mild: evidence of epithelial erosion
- Moderate: evidence of ulceration through the epithelial layer with exposed underneath tissue
- Severe: perforation

8.3.5 Ophthalmologic Assessments

The ophthalmologic assessment of IOP and slit-lamp examination to identify development or worsening of cataract will be conducted at Screening and Week 25 visits as specified in the Schedule of Assessments (Section 8.1). The cataract assessment will be conducted according to the Simplified Cataract Grading System authored by the World Health Organization Cataract Grading Group. Subject's eyes will be dilated with mydriatics following the WHO guidance for cataract assessment.^[42] IOP may be measured using Goldmann applanation tonometer, noncontact tonometer, or tono-pen; however, it is recommended that the same method be used for consistency across serial assessments on a given subject. IOP assessment will also be performed at Week 4 and 12 visits. A clinically significant increase of IOP is defined as IOP in 1 or both eyes >23 mm Hg or an increase of IOP from baseline in 1 or both eyes \geq 10 mm Hg. Assessments will be conducted by an ophthalmologist/ optometrist that is blinded to the subject's treatment assignment.

8.3.6 SCS rescue

Oral steroids for rescue treatment of CRS or intravenous or oral steroids for another reason that are prescribed to the subject are to be recorded in the eCRF. All efforts should be made to complete the Week 25 assessments including nasal endoscopy and CT before starting treatment with SCS. However, the subject should continue with the study treatment and follow-up visits. The investigator (or designee) will record the dates and dosing information (dosage form, daily dose, duration, name of drug) on the appropriate page(s) of the eCRF. Indication for SCS use will also be captured. A course of SCS is considered continuous if treatment is separated by less than 7 days.

8.3.7 Sinonasal surgery (actual or planned) for CRS

For subjects who have a surgery or have a scheduled date for sinonasal surgery as rescue for CRS, the reason (worsening signs and/or symptoms during the study), the date the surgery was indicated, expected or actual surgery date, and the type and outcome of surgery will be recorded in the eCRF. Types of sinonasal surgery include, but are not limited to, repeat FESS, balloon sinuplasty, turbinate reduction, septoplasty or polypectomy, or any endoscopic procedure that results in sinonasal tissue removal.

If the surgery is to be performed during the study treatment period, the study treatment will be discontinued and all procedures/assessments for the Week 24/EOT visits will be completed prior to the surgery. Additionally, all efforts should be made to complete the Week 25 assessments including nasal endoscopy and CT prior to the surgery. The subject will be discontinued from the study.

If the surgery is scheduled after the planned end of study, the investigator (or designee) should follow-up with the subject on the occurrence and outcome of the surgery until the time of database closure for the study.

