If **spontaneous dislodgement of LYR-220** occurs before the scheduled Week 24/EOT visit, subjects are required to call the study clinic immediately to report the event. If a subject experiences dislodgement of 1 of the bilateral matrices, the subject will continue in the treatment phase unless an early treatment discontinuation is recommended by the treating physician or subject requests matrix removal from the remaining side of the nose. If matrices spontaneously dislodge from both sides of the nose, the subject will complete an unscheduled **early-termination (ET)** visit within 7 days of the second matrix dislodgement, and complete the assessments scheduled for the Week 24/EOT visit. Spontaneously dislodged LYR-220 should be retained, if available, and returned to the clinic at subject's next visit.

If medically warranted according to the treating physician's discretion (for example, needing sinonasal surgery as rescue treatment), early matrix removal may be performed at an unscheduled ET visit.

Any subject who undergoes an ET visit is required to complete the assessments scheduled for the Week 24/EOT visit and should stay in the study and complete the assessments scheduled for the Week 25 visit within 5-9 days after the ET visit.

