4.3 Discontinuation of Study Subjects

Subjects will be encouraged to complete the study through the post-treatment follow-up period. Each subject is free to discontinue from the study at any time, for any reason, and without penalty or loss of benefit. Participation in the study treatment may be discontinued for any of the following reasons:

- Occurrence of any medical condition or circumstance that exposes the subject to substantial risk and/or does not allow the subject to adhere to the requirements of the protocol, including early removal of LYR-220 (Section 6.5).
- Any serious AE (SAE, Section 8.3.11.2), clinically significant AE, severe laboratory abnormality, intercurrent illness, or other medical condition that indicates to the Investigator that continued participation is not in the best interest of the subject.
- Subject's decision to withdraw.
- Requiring sinonasal surgery as rescue treatment.
- If deviations to the use of prohibited medications occur during run-in and study treatment periods, the Investigator, in consultation with the Sponsor and Sponsor's medical monitor will decide on a case-by-case basis whether the subject may continue in the study based on the time the prohibited medication was administered and its pharmacology.
- Subject's failure to comply with protocol requirements or study related procedures.
- Termination of the study by the Sponsor or a regulatory authority that has provided approval to proceed.

Subjects who withdraw or are withdrawn from the study treatment will be requested to return to the clinic for the assessments and procedures scheduled for the EOT and EOS visits (Section 8.1).

The Investigator or study staff will document the reason(s) for subject discontinuation on the electronic Case Report Form (eCRF), notify the EC/IRB as required by their Institution's procedures, and notify the Sponsor of the reason for discontinuation.

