Enrolled subjects will be asked to complete a daily ePRO questionnaire to assess the severity of the 4 CS of CRS (nasal blockage/obstruction/congestion, facial pain/pressure, anterior/posterior nasal discharge, and loss of smell). In addition, the ePRO will capture use of daily saline irrigation by the subjects. Subjects will also complete 2 validated CRS-specific quality of life questionnaires, the SNOT-22 and CRS-PRO, at Screening, on Day 1 before treatment, and at Weeks 2, 4, 6, 8, 12, 16, and 20, at Week 24 before matrix removal, and at Week 28/EOS. CRS-PRO will also be assessed at Day 8 and Week 3. The PGIS will be administered on Day 1

(pretreatment) and at Weeks 8, 16, and 24/EOT. The PGIC will be assessed at Week 24/EOT. At Week 28/EOS visit, an end-of-study questionnaire will be administered.

Ethmoid cavity opacification will be assessed by CT scans obtained during Screening (or using a historical scan taken within 3 months of Screening) and at Week 25 visit, unless medically contraindicated. Subjects will be instructed to stop use of saline rinse approximately 24 hours prior to the scheduled sinus CT. Daily saline irrigation should then continue following the sinus CT. If a subject is experiencing or recovering from a cold, acute exacerbation of nasal allergy, or upper respiratory tract infection at Week 25 visit, the CT assessment should be performed 4 weeks after resolution of the adverse event. If a subject early terminates from the study or requires SCS or sinonasal surgery as rescue treatment during the study, every attempt should be made to perform the follow-up CT before subject receives the rescue treatment.

LYRA THERAPEUTICS, INC. STUDY LYR-220-2021-001

VERSION 4.0 (30 AUG2022)

Enrolled
jects
Sub
s for
Assessment
$\mathbf{0f}$
hedule
Sc
Ξ
Table

		2															
		_						Treat	Treatment Stage	age						Post-	4
Evaluation	ing & Run-In	dure Day														Treatment Stage	ient je
Visits #	1	2	3	~	4		⊢	⊢	5	⊢	F	9	7/7	F	œ	6	10/T p
Study Day/Week	DAY - DAY - 28 (Day - 28 to Day 0)	DAY 1 (Day 1)	DAY 2 (Day 2)	DAY 3 (Day 3)	DAY 5 (Day 5)	DAY 8 (Day 8)	WK 2 (Day 15±1)	WK 3 (Day 22±2)	WK 4 (Day 29±3)	WK 6 (Day 43±3)	WK 8 (Day 57±3) ª	WK 12 (Day 85±3)	WK 16 (Day 113±3) ª	WK 20 (Day 141±3) ª	WK 24/EO T/ET (Day 169±7)	WK 25 (5-9 days after T)	WK 28 (EOS) (25-31 days after EOT)
Informed Consent	×c																
Demographics	×																
Medical History	Х																
Vital Signs	Х																

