Strict subject withdrawal/discontinuation criteria will also apply (Section 4.3 Discontinuation of Study Subjects) including any SAE, clinically significant AE, severe laboratory abnormality, intercurrent illness, or other medical condition that indicates to the Investigator that continued participation is not in the best interest of the subject. Subjects will be withdrawn from the study if they require surgical intervention to manage their CRS symptoms.

Prior and concomitant medications criteria are specified (Sections 6.4.2 Prohibited Concomitant Medications and 6.4.3 Permitted Concomitant Medications) to avoid confounding the safety,

pharmacokinetics, and efficacy assessments of LYR-220. Specific rescue medications are recommended for worsening of CRS symptoms that last for a minimum of 3 days and resulted in the subject contacting the Investigator (Section 6.4.4 Rescue Concomitant Medications).

In the Phase I and Phase II clinical studies of LYR-210, no AEs were associated with drug matrix dislodgements. In this study, if spontaneous dislodgement of LYR-220 occurs before the scheduled removal visit at Week 24, subjects are required to call the study clinic immediately. Subject will remain in the study unless an early treatment discontinuation is recommended by the treating physician, or subject requests matrix removal from the remaining side of the nose, or matrices spontaneously dislodged from both sides of the nose (Section 4.1.2 Treatment Stage).

Only Investigators with substantial experience in endoscopic interventions will be allowed to participate in the Study. Once selected, Investigators will undergo product-specific training prior to enrolling subjects.

Through a systematic analysis of relevant commercially approved MF drugs and based on the Phase I and Phase II clinical results of LYR-210 and the safety assessments and measures implemented in this clinical trial, the potential benefits of LYR-220 outweigh the potential associated risks and support conducting the proposed Phase II clinical trial.

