#### 2.2.4 Discontinuation of Study Subjects

Subjects will be encouraged to complete the study through the post-treatment follow-up period. Each subject is free to discontinue from the study at any time, for any reason, and without penalty or loss of benefit. Participation in the study treatment may be discontinued for any of the following reasons:

- Occurrence of any medical condition or circumstance that exposes the subject to substantial risk and/or does not allow the subject to adhere to the requirements of the protocol, including early removal of LYR-220.
- Any serious adverse event, clinically significant adverse event, severe laboratory abnormality, intercurrent illness, or other medical condition that indicates to the Investigator that continued participation is not in the best interest of the subject.
- Subject's decision to withdraw.
- Requiring sinonasal surgery as rescue treatment.
- If deviations to the use of prohibited medications occur during run-in or study treatment periods, the Investigator, in consultation with the Sponsor and Sponsor's medical monitor will decide on a case-by-case basis whether the subject may continue in the study based on the time the prohibited medication was administered and its pharmacology.
- Subject's failure to comply with protocol requirements or study related procedures.
- Termination of the study by the Sponsor or a regulatory authority that has provided approval to proceed.

Subjects who withdraw or are withdrawn from the study treatment will be requested to return to the clinic for the assessments and procedures scheduled for the EOT and EOS visits.

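### Protocol 8.3.7 and Section 11 conflict with 4.3 and 4.1.3 on follow-up after rescue surgery during treatment, so new adverse events could go uncollected for part of the SAP's 31-day window

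*Protocol*

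**What the plan says.** Two groups of sections deal with the same event.

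**Leaving the study.** Protocol 8.3.7 covers surgery performed during the treatment period. Study treatment stops, the Week 24/EOT procedures are completed before surgery, and best efforts are made to complete the Week 25 assessments before surgery. It then says "The subject will be discontinued from the study". SAP 3.6.7 carries the same text. Protocol Section 11 says "Subjects will be withdrawn from the study if they require surgical intervention to manage their CRS symptoms". None of these mentions EOS.

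**Leaving treatment but not follow-up.** Protocol 4.3 lists rescue surgery among the reasons for stopping study treatment and says that subjects withdrawn from treatment "will be requested to return to the clinic for the assessments and procedures scheduled for the EOT and EOS visits". SAP 2.2.4 repeats both the reason ("Requiring sinonasal surgery as rescue treatment") and the request. Protocol 4.1.2 gives rescue surgery as its example of medically warranted early removal and says that any subject with an ET visit "should stay in the study and complete the assessments scheduled for the Week 25 visit within 5-9 days after the ET visit". Protocol 4.1.3 plans a Week 25 visit for all subjects and a further contact four weeks after treatment, at which AEs are collected. It makes no exception for surgery.

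Protocol 8.3.6, immediately before 8.3.7, is explicit for steroid rescue: "However, the subject should continue with the study treatment and follow-up visits". Section 8.3.7 has no matching sentence.

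**The concern.** The trial's primary objective is safety. SAP 3.6.1 counts TEAEs and TESAEs that start up to 31 days after study treatment is discontinued, and the SAP's primary endpoint, product-related TESAEs (2.3.1 and 3.1.4.1), uses that definition. Under Protocol 8.3.11.6.1, however, AEs are collected only until a subject's follow-up visits are complete. Ending a subject's participation early therefore ends planned collection of new events early.

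The tables would not show the shortfall. Protocol 9.6 and SAP 3.6.1 report numbers and percentages of subjects with events, and Protocol 9.6 specifies no imputation. A subject not observed for part of the window stays in the denominator as someone without an event. Surgery recommendation is also part of an endpoint compared between arms (SAP 3.4.2.6), so if surgery rates differed, the length of AE follow-up would differ by arm as well.

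**Working it through.** The plan gives no figure of its own here, so the check is a day count.

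**Inputs**
- TEAE/TESAE window: 31 days after discontinuation of study treatment (SAP 3.6.1).
- Week 25 assessments: 5-9 days after ET (Protocol 4.1.2).
- EOS contact: 25-31 days after EOT (Protocol 8.1, Table 1); telephone is allowed (Table 1 footnote; 4.1.3).
- Assumption: study treatment is discontinued on the day of EOT/ET (day 0), and ET counts as EOT for timing EOS, because Table 1 puts them in one column.

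**Formula.** If the last contact at which AEs are collected falls on day d after ET, the uncovered part of the window is 31 − d days.

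| Last contact | d | Uncovered days | Share of 31 days |
|---|---|---|---|
| Week 25 | 5 to 9 | 31 − 9 = 22 to 31 − 5 = 26 | 71% to 84% |
| EOS | 25 to 31 | 31 − 31 = 0 to 31 − 25 = 6 | 0% to 19% |

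More than half the window is uncovered whenever d is below 31 / 2 = 15.5, which holds across the whole Week 25 range. Compared with an EOS contact, stopping at Week 25 gives up between 25 − 9 = 16 and 31 − 5 = 26 days of follow-up.

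**What the count depends on.** The Week 25 row requires that study discontinuation takes effect once those assessments are done. Protocol 8.3.7 does not say when it takes effect. If contact with AE collection continued to a surgery date on day 20, for instance, 31 − 20 = 11 days would be uncovered.

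**Which events are exposed.** Only events with onset after the last contact. Ongoing AEs that led to early termination, or that are judged related to product or procedure, are followed until they resolve or stabilize (8.3.11.1). For SAEs already identified, reports continue until resolution or, with permanent impairment, stabilization (8.3.11.6.2). Steroid-rescue subjects are unaffected (8.3.6).

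**The case against.** The strongest reply is that the documents already answer the question. Section 4.3 governs discontinuation, names rescue surgery and requests EOS; SAP 2.2.4 agrees; 4.1.3 plans the Week 28 contact without exception; and the Section 11 paragraph refers back to 4.3. Silence in 8.3.7 does not cancel an express request elsewhere. That stands: a site reading all these sections together would make the EOS contact and cover most or all of the window. It does not remove the conflict, because 8.3.7 is the section specific to surgery. Recording the surgery's outcome, as 8.3.7 requires, implies some later contact, but no AE collection is attached to it.

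Three stronger readings are tempting, and the documents do not support them.
- A reader might infer that the plan leaves these subjects with no AE follow-up at all after removal. Sections 4.1.2 and 4.1.3 plan Week 25 and 8.3.7 asks for best efforts to complete it, so the full 31 days would be uncovered only if Week 25 were missed or done on the day of removal and contact then ended.
- A reader might infer from 8.3.11.2, under which follow-up of a treatment-related SAE can end when the subject withdraws, that known SAEs would be dropped. Section 8.3.11.6.2 requires reports on them to continue.
- A reader might infer a demonstrated loss on the primary endpoint. Only a new, serious, product-related event arising after the last contact would count, and no estimate is shown to change.

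It is also fair to say that the SAP's 31 days limits which events are counted and does not promise 31 days of observation for everyone. Even with EOS, up to 6 days can remain uncovered.

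**Conclusion.** The instructions conflict, and the conflict is worth resolving. Protocol 8.3.7, Section 11 and SAP 3.6.7 take a rescue-surgery subject out of the study without mentioning EOS; Protocol 4.3, 4.1.3 and SAP 2.2.4 keep an EOS contact. A site that acts on the first group could stop collecting new-onset AEs early. On a worst-case reading of when discontinuation takes effect, with Week 25 as the last contact, 22-26 of 31 days are uncovered per affected subject, against 0-6 days with EOS.

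This rests on treating ET as EOT and on discontinuation taking effect after Week 25, which the protocol neither states nor rules out. The documents do not give the number of subjects affected, and it may be zero. The defect is an inconsistency with a possible effect on safety capture, not an established gap in the data.

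**What to change.** In Protocol 8.3.7 and Section 11, and in the copy in SAP 3.6.7, state that rescue surgery ends study treatment, and that AEs, SAEs and concomitant medications/procedures are still collected through the EOS contact 25-31 days after EOT/ET, in line with 4.3 and 4.1.3, by telephone if needed, unless the subject withdraws consent.

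The cost is about one sentence in each of the three places and one contact per affected subject. That contact is already in Table 1 and may be made by telephone, so no new visit is added.
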